### **2.6. Safety**

Participants will be provided with a tracking sheet to note any adverse events (AEs) throughout the study. The instructors will also monitor for adverse events during the in-person sessions. If any AE happens, participants will be instructed to tell the instructor to modify the exercises or reduce the intensity if necessary. AEs will be defined as any problem that lasts for >2 days and/or causes the participant to seek other treatment.

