### 2.3. Screening and assessments

Potential participants will contact the research team through the contact information provided in the flyer and study poster. Screening will be conducted over the telephone and study information will be provided. Consenting and eligible participants will be sent an individualized link to the written consent form, written study information, and baseline

questionnaires. Those who pass the screening, including exercise safety, will be invited to an in-person physical assessment. Upon program completion, participants will be sent the questionnaires again (which also include the exit survey questions) and will attend a second in-person assessment of physical measures. Focus groups will be conducted to further assess the participants' perception of the study. If a participant has bilateral KOA, the most symptomatic knee will be studied. If both knees are equally affected, the dominant knee will be studied, which is the knee with which the individual steps first when initiating gait.

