#### **2.4. Randomization and blinding**

Participants will be randomized with an allocation ratio of 1:1 into one of two treatment groups (Pain Informed Movement or neuromuscular exercise and standard OA education) using a REDCap randomization module. The process of randomization will be conducted by a member of the research team who is independent of the recruitment process. Additionally, the assessors responsible for conducting baseline and follow-up assessments will be blinded and not involved in recruitment. Blinding of exercise instructors is generally not possible in studies of physical interventions (e.g., exercise) [21]. Participants will be blinded to study hypotheses and the two treatment groups. As both arms of the study are providing exercise-based interventions and education, participants will be provided limited details of each intervention arm so as to blind them from knowing which is the intervention and which is the control. This will help minimize any bias that occurs by knowledge of group assignment and perception of treatment effects.

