Part two: of the second part is the main exercises (based on the original NEMEX-training program [4]) This part is divided into four sections: core stability, postural orientation, lower extremity muscle strength, and functional exercises with an emphasis on proper alignment of the knee over the foot. Within each section, there are two types of exercises and three levels for progression. Participants will be instructed to complete each exercise for two to three sets of eight to 15 repetitions. For the core stability section, one exercise is instructed based on breaths. When an exercise is performed with good quality of the performance, with minimal exertion, and with control of the movement, it can be progressed by increasing repetitions or the load (going through the levels). The exercises will be performed with both the affected and the unaffected leg.

Part three: the third and last part is cooldown which consists of the same warmup movements plus relaxation and guided self-reflection. Participants will be cued to use the PNE concepts and mind-body techniques during the exercise sessions.

Participants will also complete a third home session (weekly) which is facilitated by handout sheets. The exercise component will be delivered by an experienced yoga teacher with training in the integration of pain science and mindful movement.

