### **2.5.2. Neuromuscular exercise and standard OA education**

Participants in this group will receive an 8-week in-person group exercise program held twice weekly, in which they will receive exercise instructions and standard OA education. Participants will be provided with tracking sheets to note their compliance and progress.

The exercise component (60 min) of this group will be similar to that of the other group without the added mind-body techniques. Similarly, a third home session (weekly) will be facilitated by exercise handout sheets. The exercise instructions will be delivered by a physiotherapist. The standard OA education will consist of several short videos (20–30 min/week for the first two weeks provided through online videos) and will cover the following topics: pathophysiology of OA, common OA symptoms, risk factors, the effects of exercise, and self- management tips. Participants will be given the opportunity to ask questions during the in-person sessions.

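### Adverse events are gathered by a self-kept sheet and by unblinded instructors who differ by arm; a common prompted question at follow-up and reporting by source would be a cheap improvement

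*Combined protocol and SAP*

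**What the plan says.** Section 2.6 (Safety) describes two ways in which an adverse event reaches the study record. The first is the participant's own record: "Participants will be provided with a tracking sheet to note any adverse events (AEs) throughout the study". The second is the instructor: "The instructors will also monitor for adverse events during the in-person sessions". If an event occurs, "participants will be instructed to tell the instructor to modify the exercises or reduce the intensity if necessary", so spoken reports also go to the arm's own instructor. One definition serves both arms: "AEs will be defined as any problem that lasts for >2 days and/or causes the participant to seek other treatment".

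The instructor differs by arm. Section 2.5.1 says "The exercise component will be delivered by an experienced yoga teacher with training in the integration of pain science and mindful movement", with a 75-minute exercise component. Section 2.5.2 says "The exercise instructions will be delivered by a physiotherapist", with 60 minutes. Both programs run twice weekly for 8 weeks, plus one weekly home session. Section 2.4 accepts that "Blinding of exercise instructors is generally not possible in studies of physical interventions (e.g., exercise". The outcome assessors are blinded, and participants are to be blinded to the hypotheses and to which program is the intervention.

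On follow-up, section 2.3 says "Upon program completion, participants will be sent the questionnaires again (which also include the exit survey questions", together with a second in-person physical assessment. No AE question is described there, in section 2.9 or in Table 3. The items of the exit survey are not listed.

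Adverse events are a feasibility outcome (section 2.7). Their Table 2 row asks what percentage of participants had no event or only mild transient ones, and it is not split by arm. Section 2.11 reports feasibility outcomes descriptively.

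**The concern.** One of the two AE channels differs by arm in who observes, in that person's training and in the time available. Each instructor type belongs to one arm only, so no analysis can later separate the effect of the observer from the effect of the program. The other channel, the sheet, is common to both arms, but it relies on each participant deciding unprompted to write something down. The plan does not say how the two are combined, or whether events will be reported by source.

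Two things are at stake. The first is any tabulation of AEs by arm that includes instructor reports. Relative tolerability is a natural thing for a pilot to pass on to a main trial, and such a table could mislead in either direction. The second is closer to the plan's own rule: missed events raise the observed proportion of event-free participants and so favour 'Proceed' in Table 2.

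**Working it through.** The plan states no figure on AE ascertainment, so there is none to reproduce. The check has three parts.

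**1. The channels side by side (from the documents)**

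| Feature | Sheet | Instructor |
|---|---|---|
| Same tool in both arms | Yes | No: yoga teacher or physiotherapist |
| Period covered | Whole study | In-person sessions only |
| Blinding | Participant blinded to hypotheses and to which program is the intervention | Not blinded |
| Prompted by a standard question | None described | None described |

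Scheduled in-person time is 2 × 8 = 16 sessions per arm: 16 × 75 min = 1,200 min (20 h) against 16 × 60 min = 960 min (16 h), a ratio of 1.25. Home sessions are 8 of 24, one third, in both arms. During those, the sheet is the only contemporaneous source.

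**2. Unequal capture by arm (illustration; event and capture rates assumed)**

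Let the true AE proportion be t in both arms, with capture s1 and s2 and 33 per arm. The apparent difference is t × (s1 − s2). The 95% half-width is 1.96 × √[p1(1 − p1)/33 + p2(1 − p2)/33], where p1 = t·s1 and p2 = t·s2.

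| t | s1, s2 | Recorded proportions | Spurious difference | 95% half-width |
|---|---|---|---|---|
| 0.20 | 0.9, 0.7 | 0.18, 0.14 | 0.04 | 0.18 |
| 0.20 | 0.9, 0.5 | 0.18, 0.10 | 0.08 | 0.17 |
| 0.30 | 0.9, 0.7 | 0.27, 0.21 | 0.06 | 0.21 |
| 0.30 | 0.9, 0.5 | 0.27, 0.15 | 0.12 | 0.19 |
| 0.40 | 0.9, 0.7 | 0.36, 0.28 | 0.08 | 0.22 |
| 0.40 | 0.9, 0.5 | 0.36, 0.20 | 0.16 | 0.21 |

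With no true difference, the recorded difference is 4 to 16 percentage points. In each row this is smaller than the sampling half-width of 17 to 22 points. The documents do not show which arm would have the better capture.

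**3. Under-capture and the pooled Table 2 row (illustration; assumed rates)**

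'Proceed' needs at least 75% of participants free of more than mild transient events. With all 66 counted, 0.75 × 66 = 49.5, so 50 are needed. If a proportion t truly has a disqualifying event and a proportion s of these is recorded, P(Proceed) = P(X ≥ 50), where X ~ Binomial(66, 1 − t·s).

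| t | s = 1 | s = 0.9 | s = 0.7 | s = 0.5 |
|---|---|---|---|---|
| 0.25 | 0.51 | 0.69 | 0.94 | 1.00 |
| 0.30 | 0.19 | 0.36 | 0.79 | 0.98 |
| 0.35 | 0.04 | 0.13 | 0.55 | 0.94 |
| 0.40 | 0.01 | 0.03 | 0.30 | 0.85 |

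From t = 0.30 upward the true event-free proportion is below the 75% bar, yet incomplete capture can make 'Proceed' the likely reading.

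**The case against.** The strongest reply is that the sheet already provides a common, contemporaneous, whole-study record under one definition, kept by participants who are to be blinded. That stands. A reader might infer that any AE difference between arms is confounded with who was watching; the documents do not support this, because a difference seen on the sheet alone involves no observer. What remains for the sheet is narrower. The experimental arm is taught that pain is a poor guide to tissue damage (section 2.5.1), which could change what participants consider worth recording.

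A reader might also infer that the follow-up contains no AE question at all. The documents do not show that. The exit survey items are not set out, and Table 3 lists secondary outcomes whereas AEs are a feasibility outcome. Burden and acceptability ratings are also missing from Table 3, although they must be collected somehow. 'Not described' is as far as one can go.

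Nor is a planned between-arm AE comparison being spoiled, because none is specified. The distortion would affect a descriptive table by arm, if one is produced, and at 33 per arm chance alone could produce gaps of the size illustrated.

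The AE definition also limits the contact-time argument. Duration beyond two days, or seeking other treatment, cannot be seen within one class and must come largely from the participant. The 25% difference in hours therefore describes unequal opportunity; it does not measure bias. Instructors still hear reports twice a week, so their channel is not negligible.

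Lastly, a self-completed checklist does not remove an effect of education on reporting, and eight-week recall is weaker than a contemporaneous record. Both points stand, and they are why the checklist should supplement the sheet.

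**Conclusion.** The point holds in a limited form. Instructor-sourced or combined AE counts cannot be separated from arm, because the observer's profession and session length are tied to arm and the observer is unblinded. Sheet-only counts are free of that problem but remain open to an influence of the pain education. Since no prompted question common to both arms is described, under-capture is possible, and it would move the pooled Table 2 row toward 'Proceed'.

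The size depends on assumed event and capture rates, for which the documents give no values. At an assumed 30% true rate, the chance of 'Proceed' rises from 0.19 with full capture to 0.79 with 70% capture, taking all 66 participants as the denominator and treating them as independent. The facts about instructors, session lengths and channels come directly from the protocol. This is an inexpensive improvement to a pilot's safety reporting and does not threaten the primary outcome, the follow-up rate.

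**What to change.** - Add a short structured AE checklist to the existing REDCap follow-up questionnaire, worded identically in both arms and sent to every randomised participant. Suggested items are new or worsened knee pain, other joint or muscle pain, fall, faintness and other. For each, ask the two parts of the section 2.6 definition: whether it lasted more than two days and whether other treatment was sought. If the exit survey already has such items, state this and list them.
- Use the checklist together with the contemporaneous sheet, not in place of it, for the Table 2 AE row, and state the rule for combining them. Where the questionnaire is not returned, use the sheet.
- Report AEs by arm and by source, with instructor-observed events shown separately as supporting data.

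Placing the items in the questionnaire, and not in the assessor's interview, also protects assessor blinding. The cost is a few electronic items and about two minutes per participant, with no extra visit or staff. The drawbacks are some recall error over 8 weeks and missing answers from non-responders, who may include people with AEs.

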### 2.5.1. Pain Informed Movement program

Participants in this group will receive an 8 week in-person group exercise program held twice weekly, in which they will receive exercise instructions and PNE. They will also be

asked to complete a third exercise session at home weekly. Participants will be provided with tracking sheets to note their compliance and progress.

The PNE component will consist of several short videos that are provided online for the first five weeks of the program (the videos are divided into short segments, each with a separate subject, totaling 20–30 min/week)). The videos will provide simple explanations of nociception processing by the nervous system, how it can be modulated through upregulation or downregulation of signals to increase or decrease pain and that pain does not accurately signify the extent of tissue damage, particularly when experiencing chronic pain. The videos will also offer techniques to reconceptualize pain and movement not as imminently dangerous. In addition, the videos will introduce and provide a demonstration of mind-body techniques that will be provided progressively each week. The mind-body techniques will include breath awareness and regulation, body awareness and muscle tension regulation, and awareness of pain related thoughts and emotions. The techniques will then be implemented in the in-person exercise sessions where participants are asked to incorporate them into their performance of the exercises. Instructions will be provided on how to ‘nudge the edge’ of pain which is conceptualized as a balance between challenging current physical abilities during the exercises and being successful at not leaving pain provoked and/or function limited after exercise. Participants will be instructed to use breath, body tension, thoughts, and emotions as guideposts to their pain in order to successfully nudge its edge. Participants will be given the opportunity to ask questions during the in-person sessions.

The exercise component (75 min) will consist of three parts (in sequence):

Part one: the first part is the warm-up which begins with a centering practice aimed at regulating physiology. Next, warming movements of the shoulders, legs, and spine will be instructed.

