Burden (0 = no burden, 10 = most burden)	Burden of completing questionnaires and physical tests <3/10 for ≥75% of participants	Burden of completing questionnaires and physical tests <3/10 for ≥50% of participants	Burden of completing questionnaires and physical tests <3/10 for ≤25% of participants
Adverse events	No adverse events or only mild transient (e.g., pain increase) for ≥75% of participants	No adverse events or only mild transient (e.g., pain increase) for ≥50% of participants	No adverse events or only mild transient (e.g., pain increase) for ≤25% of participants

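### Under the Section 2.6 definition, a short, non-mild problem for which no other treatment is sought scores as no adverse event in Table 2, which can only favour Proceed

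*Combined protocol and SAP*

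**What the plan says.** Section 2.6 (Safety) gives the only definition of an adverse event: "AEs will be defined as any problem that lasts for >2 days and/or causes the participant to seek other treatment". Either condition is enough. Capture is by two routes: "Participants will be provided with a tracking sheet to note any adverse events (AEs) throughout the study", and "The instructors will also monitor for adverse events during the in-person sessions". The same section adds: "If any AE happens, participants will be instructed to tell the instructor to modify the exercises or reduce the intensity if necessary".

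Table 2 in Section 2.7 turns adverse events into a progression criterion. The Proceed column reads "No adverse events or only mild transient (e.g., pain increase) for ≥75% of participants". The middle column has the same wording with a lower threshold, "No adverse events or only mild transient (e.g., pain increase) for ≥50% of participants", and the last column reads "No adverse events or only mild transient (e.g., pain increase) for ≤25% of participants".

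The documents do not define mild or transient, grade severity, or define a serious adverse event.

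Section 2.5.1 describes the experimental program's approach to pain as a balance that includes "being successful at not leaving pain provoked and/or function limited after exercise".

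**The concern.** The definition sorts problems by duration and by whether treatment was sought. The Table 2 row sorts them by severity and transience. Nothing links the two. A problem that passes within 2 days without other treatment never becomes an adverse event, so its severity is never considered and the participant falls under no adverse events.

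Adverse events are a named feasibility outcome with a stated progression rule, so this affects a decision. It also concerns what the pilot is testing: since Section 2.5.1 describes success partly by the state of pain and function after exercise, problems soon after a session bear directly on tolerability, and many of them could be short.

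The reporting instruction has a related difficulty. It is worded to start when an adverse event happens. On the day of onset, a problem for which no other treatment has been sought cannot yet have lasted more than 2 days, so it is not yet an adverse event and the instruction does not literally apply.

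**Working it through.** The plan states no figure for this point that could be reproduced. The check sets the definition against the Table 2 row and then asks whether the difference can change the decision.

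**Step 1: classify problems.** The inputs are the Section 2.6 definition and the Table 2 row.

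| Problem | Adverse event under 2.6? | Scored in Table 2 as written | If recorded and graded |
|---|---|---|---|
| (a) 2 days or less, mild, no other treatment sought | No | Favourable (no event) | Favourable (mild transient) |
| (b) 2 days or less, not mild, no other treatment sought | No | Favourable (no event) | Not favourable |
| (c) 2 days or less, other treatment sought | Yes | Reaches the row | Reaches the row |
| (d) More than 2 days | Yes | Reaches the row; class depends on undefined terms | Reaches the row |

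Only type (b) is scored differently. Leaving it out can keep a participant in the favourable category but can never remove one, so the error can only raise the percentage.

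**Step 2: turn the threshold into counts.** The planned sample size is 66 (Section 2.2). Table 2 does not state the denominator, so all 66 is an assumption. Proceed needs at least 0.75 × 66 = 49.5, that is 50 participants, in the favourable category. At most 66 − 50 = 16 may fall outside it.

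**Step 3: effect on the row.** Let m be the number of participants with a captured event that is not mild and transient, and k the number of further participants whose only non-mild problems are of type (b).

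- Share as written: (66 − m)/66
- Share with type (b) counted: (66 − m − k)/66

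The documents give no expected event rates, so m and k are assumed over a range.

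| m | As written | k = 3 | k = 7 |
|---|---|---|---|
| 10 | 56/66 = 84.8% | 53/66 = 80.3% | 49/66 = 74.2% |
| 14 | 52/66 = 78.8% | 49/66 = 74.2% | 45/66 = 68.2% |
| 16 | 50/66 = 75.8% | 47/66 = 71.2% | 43/66 = 65.2% |

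The row leaves Proceed when m + k reaches 17, so the k needed is 17 − m: 7 participants at m = 10, 3 at m = 14 and 1 at m = 16. In every cell below 75% the result moves to the middle column.

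**Step 4: the reporting instruction.** On the day of onset the duration condition cannot be met. Unless other treatment has been sought, neither condition holds, so the trigger in the sentence is not met.

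**The case against.** The strongest reply is that the two sections can be read together. Transient is undefined, so a mild pain increase that lasts 3 or 4 days and then settles is an adverse event under Section 2.6 and can also be mild transient under Table 2. That is fair. A reader might infer that transient must mean 2 days or less, so that the Table 2 category is empty by definition; no text says so. What stands is that the terms are undefined and that type (b) problems are lost on either reading.

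A reader might also infer that short events, even serious ones, can never reach the criterion. The definition does not support this: a problem of any duration counts once it causes the participant to seek other treatment, and many serious events would qualify that way. The gap for serious events is the absence of severity and seriousness rules.

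Nor do uncounted mild flares bias the row. No event and only mild transient events share one favourable category, so a short mild flare scores the same counted or not. Differing counts between sites cannot arise either, because Section 2.1 describes a single-centre trial.

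On the reporting sentence, it can be said that instructors see participants twice a week and that nothing forbids adjusting exercises for a problem that is not yet an adverse event. That is true, and no loss of data is shown to follow. It remains a wording conflict within Section 2.6.

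Finally, pain scores, KOOS, ICOAP, the exit survey and the focus groups also bear on tolerability. They are collected at baseline and follow-up, or at follow-up only, and they do not feed the adverse event row.

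**Conclusion.** The concern holds in a limited form. Section 2.6 and the Table 2 adverse event row use different criteria, the severity terms are undefined, and a short, non-mild problem for which no other treatment is sought is scored as no adverse event. The resulting error goes in one direction only, towards Proceed.

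Its size depends on event counts that the documents do not give. With a denominator of 66, between 1 and 7 such participants are enough to move the row out of Proceed when 16 down to 10 participants already have captured non-mild events. If captured events are few, many more would be needed (17 if there are none), and the gap would probably not matter. The calculation assumes that short mild problems would be graded mild transient and that the type (b) participants are not already outside the favourable category.

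The reporting sentence is a secondary point of wording. The change should be made because it is cheap and removes a one-sided bias from a stated progression criterion; the point does not call the trial's safety monitoring as a whole into question.

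**What to change.** - In Section 2.6, have the existing tracking sheet record any new or worsened problem of any duration, with onset, duration, severity, seriousness and whether other treatment was sought. State how severity and seriousness are classified.
- Keep the present rule (more than 2 days, other treatment sought, or both) as a flag marking a subset, so that it can still be reported.
- In Table 2, define mild and transient from the recorded fields, so that a short, non-mild problem counts against the criterion. State the denominator of the row.
- Reconcile the sentence on telling the instructor with the definition, so that the two agree on what triggers it on the day a problem starts. The content of that rule is for the trial team.

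The cost is a wording change in two places and a few extra columns on the sheet. More minor problems will be logged and the reported number of adverse events will be higher; the flagged subset shows what the present rule would have counted.
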